4.2.2 Intervention – IDC group

IDC (Arm1) participants will be informed they have periodontitis and invited to attend a series of visits (BDH or DFS-GDPr). These appointments may be at Bristol Dental Hospital (BDH), or at a Dental Foundation Scheme-General Dental Practice (DFS-GDPr) accredited to provide postgraduate training to Dental-Foundation-Trainees. Each DFS-GDPr has an appointed, accredited and salaried educational supervisor (ES) responsible for the training of the DFT. The study dental nurse will allocate the study participant to BDH or a DFS-GDPr taking travel time into account as far as possible. Periodontal treatment for these participants will be free of charge.

Dentists providing the intervention for the IDC (Arm1) participants (and ESs) will be given appropriate training/update training in the diagnosis, treatment planning and management of participants according to current UK guidelines [67], and the motivational techniques used successfully previously by the research team to improve participant compliance with oral hygiene regimes. A video of the intervention protocol (below) will also be made and provided for reference. Copies of dental charts taken as routine during the treatment of periodontitis will be provided to the study team.

Prior to implementing the IDC protocol a full periodontal assessment (<2 weeks post-randomisation) will determine the treatment plan and visits required to reach periodontal health (3-5 within the first 3-months).

IDC protocol:

- 1. Behaviour motivation and support for participants to attain and maintain effective plaque removal and reduce gum inflammation by a personalised, tailored oral hygiene regimen and motivational advice to maximise home-compliance [26,69].
- 2. Reduce/eliminate subgingival plaque and calculus with standard mechanical therapies and antibiotics if indicated clinically.
- 3. Address sites that respond poorly by repetition of standard mechanical treatment therapies and/or surgical interventions.
- 4. Deliver supportive periodontal care per current UK-guidelines [67] to maintain oral health

If participants in this arm (IDC) have a dentist we will inform the practitioner of their patient's participation in the study; the participant will attend our sites for the IDC, but their GDP for other routine care. The IDC will be free, and the patient should not incur any additional costs from their regular practice.

Participants will receive study-related 'reminders' throughout their participation, advice on the nature of these reminders will be sought from the PPI-lead/PAG.

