Dissemination: Throughout, we will keep everyone informed by means of talks, publications and social media posts. Slowing the progress of Alzheimer's by improving dental health could dramatically improve quality of life for sufferers and carers. If the study provides evidence to support a larger trial and shows the personalised dental care plan is helping, we would be able to strongly recommend the use of a personalised dental plan for the treatment of Alzheimer's patients within existing frameworks of care.

STUDY SUMMARY

Study Title	Feasibility study: Can reducing periodontal infection (gum disease) slow the progression of cognitive impairment associated with Alzheimer's disease
Short title	Oral Health for Brain Health
IRAS Number	315223
Sponsor ref. no.	DE/2021/7205
Study Design	An examiner blind, parallel, 2 arm randomised controlled trial in adults with early-stage-Alzheimer's Disease or Mild Cognitive Impairment (MCI), who also have periodontal disease. Participants will be randomised to an intensive or standard dental intervention.
Study Participants	Adults with early-stage-Alzheimer's Disease (AD) or Mild Cognitive Impairment (MCI), who also have periodontal disease
Planned Size of Sample (if applicable)	50
Follow up duration (if applicable)	Up to 18 months
Planned Study Period	September 2022 – May 2025
Research Question/Aim(s)	Overarching Aim:
	To show whether improved periodontal health can slow the progression of Alzheimer's Disease (AD).
	Aim of this feasibility trial:
	To assess the feasibility of conducting a Randomised Controlled Trial (RCT) of an Intensive Dental Care intervention (IDC), compared with the Standard Dental Care (SDC) provided in General Dental Practice, in AD patients to slow down decline in cognitive function
Key words	Alzheimer's Disease, cognitive decline, periodontal (gum) disease, oral health

FUNDING AND SUPPORT IN KIND

FUNDER(S)	FINANCIAL AND NON FINANCIALSUPPORT		
(Names and contact details of ALL GIVEN			
organisations providing funding and/or			
support in kind for this study)			
National institute for Health Research	Research costs: £261,791.00		
(Research for Patient Benefit): NIHR203048 NHS support and treatment costs: £11,443			

ROLE OF STUDY SPONSOR AND FUNDER

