4. STUDY DESIGN

4.1 Overview

A feasibility study of a multi-site RCT of a dental care intervention for people with early-stage-AD or Mild Cognitive Impairment (MCI), who also have periodontal disease, in which the following definitive trial will investigate differences in rate of cognitive decline.

- Intervention group (Arm1): treated with IDC.
- Control group (Arm2): continue with SDC.

IDC (Arm1) comprises treatment for periodontitis, and oral hygiene instruction tailored for the individual, delivered using motivational techniques in general dental practice or secondary care by dentists on training pathways (up to 10 sites). SDC (Arm2) is the standard of dental care provided by the general dental services, participants in this group will be asked to continue with their normal dental care practices.

The 2 groups will be assessed at baseline, 6- and 12-months for cognitive and periodontal status by central research team study staff at study appointments that are independent of study intervention appointments. Patient flow through the study is shown in the study flow chart (Figure 1) above and the consort diagram (Figure 2), below.

Few RCTs have assessed adherence to oral hygiene regimens for longer than 6-months, but successful outcomes at 12-months have been reported [68]. In a pilot study of AD patients given an oral hygiene intervention similar to IDC (carried out by this research team), improvements in oral health were achieved and maintained at 12-months even though there was slow, steady cognitive decline indicating that this measure is sensitive to change in this timeframe. Within the 3-year funding timeframe it is not possible to collect data from all participants beyond 12-months, however cognitive data at 18-months will be collected from as many as possible (~75% participants).

Figure 2: Consort diagram of patient flow through the study (data based on pilot study)

Samples of blood and saliva will be collected from all participants at screening/baseline, 6 and 12 months and analysed for inflammatory markers and bacterial composition and load.

Qualitative work to assess the acceptability of the IDC/study design to participants and dentists will also be undertaken.

Definition of End of Study

The end of the study is defined as the completion of the analysis of blood and saliva.

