4.2 Study visits

4.2.1 Screening (post informed consent) and baseline assessment

Participants who have consented to take part in the study will first be assessed for eligibility against cognitive inclusion/exclusion criteria (in addition to the already assessed capacity to consent). The study dentist will then assess eligible volunteers for dental inclusion/exclusions. Participants meeting all inclusion criteria and none of the exclusion criteria will be enrolled. Baseline scores of cognitive and periodontal status will then be completed and samples of blood and saliva taken for inflammatory markers. All participants will receive oral and written oral hygiene education, toothpaste, a power toothbrush and an appointment to return to the Brain Centre after 6-months.

Immediately post the screening appointment, once baseline cognitive and periodontal status results can be combined, a Stratified Randomisation Schedule (computer-generated, concealed from recruiter until consent obtained) will be used to randomise participants to IDC(Arm1) or SDC(Arm2) stratified by cognitive status (MCI or early AD) and periodontal status (mild or severe). Participants will be contacted by their preferred method to confirm their randomisation to Arm1/Arm2.

As participants who do not meet screening criteria may be disappointed, they will be advised about other opportunities to become involved in research, such as participation in Patient Advisory Groups, or other studies that they may be eligible to take part in.

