4.3 Assessments

Baseline, 6 and 12 months:

- Cognitive assessment: Clinical Dementia Rating Sum of Boxes (CDR-SB): an appropriate and widely used primary outcome measures for early and late dementia [71]. Alzheimer's Disease Assessment Scale Cognitive subscale (ADAS-Cog11) [72], and Bristol Activities of Daily Living Scale (BADLS), measuring functional ability [73].
- Periodontal assessment: Bleeding on Probing (BOP) (yes/no); periodontal pocket depths (mm)four gingival sites/tooth; dental plaque- O'Leary plaque index (yes/no)-four surfaces/tooth [74].
- Blood/saliva (laboratory research): Assessed for inflammatory response and bacterial load to confirm that bacteraemia and that pathogens have been reduced by the treatment.

18-months (cognitive only):

 Cognitive assessment: ADAS-Cog assessment over video. This assessment has been adapted and used successfully by the team in a recent previous study during the covid-19 pandemic. There is a precedent for comparing video and face-to-face ADAS-Cog, although this is not yet validated or mainstream. This assessment will not be audio-recorded, the assessor will record scores in the same way as they would in a face-to-face scenario.

Both the study dentist and cognitive assessor will be blinded to the treatment received by the participant.

Qualitative assessments (measuring impact on participants/dentists)

These assessments will be undertaken by the central research team at 12-month visit(participants), or on-line via Zoom/similar once the treatment course(s) is/are complete for their participants (dentists who delivered IDC):

In-depth, semi-structured, qualitative interviews will be carried out with 10-12 participants (5-6 from the control and 5-6 from the intervention group) as well as up to 8 of the dental teams who delivered the intervention. Interviews will follow a topic guide that will assess participants' acceptability of the intervention, barriers and facilitators to participation, the ingredients of the intervention that they felt had positively or negatively impacted on their behaviour and overall perceptions about the feasibility of the study. Dental teams will be asked similar questions, in addition to questions aimed to assess treatment fidelity with regard to the motivational intervention. Interviews will be audio-recorded and fully transcribed. It is expected that these will take about 30 minutes for each patient participant and 15 minutes for each dental practitioner.

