6.3.2 Consent

Participants who have expressed an interest in taking part in the study will be sent a copy of the participant information sheet prior to their study appointment in the format that they prefer (paper, electronic). At screening participants will attend Southmead Hospital (Brain Centre) so that dental and cognitive assessments can be performed in a single visit. Prior to any study procedures the cognitive assessor will go through the participant information sheet and take informed consent from the participant with the project partner/carer present, excluding individuals lacking capacity. Informed consent will be captured in written form, and captured on the Easy-read consent form where participants have initially received the Easy-read PIS due to language.

This study involves adults with AD, however we will only enrol those with capacity to consent. While a project partner will be recruited, they will not have to attend every study appointment as this is often not practical or necessary for those with early-stage cognitive-decline; in the pilot study project partners and participants requested that the requirement for the project partner to be present at all participant visits was removed. The project partner will be required to attend the screening appointment before capacity to consent has been confirmed. During the consent process the participant's capacity to consent and ability to (1) retain information long enough to make a decision, (2) understand what the decision relates to and consequences of not deciding, (3) understand the benefits, risks and inconveniences of study-participation, (4) communicate their decision, will be assessed. An autonomous informed and written consent form documenting the patient's decision to participate in the study will be completed prior to screening for study inclusion.

Where the individual's capacity to consent is in doubt, every effort will be made to maximise capacity using simple language/leaflets/drawings. Consent will only be obtained if the clinical psychologist believes the individual is competent to consent.

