8. ETHICAL AND REGULATORY CONSIDERATIONS

8.1 Assessment and management of risk

The qualitive assessments (semi-structured interviews) will be undertaken by staff trained by the senior qualitative researcher, questions will not be of an upsetting or disturbing nature, they will simply explore the perceptions of participants receiving the intervention and dentists providing the intervention of its success. Participants will be asked to consent to be approached to take part in the qualitative research when they give informed consent at the start of the study, and both groups will give informed consent for the qualitative research prior to taking part in this. It is highly unlikely that the researcher would come into information that has safeguarding implications.

As indicated in '6.3.2 consent' above, this study will recruit those who have cognitive decline, but clear consent procedures are in place to ensure only those with capacity are recruited, and there are also procedures that will be followed if participants lose capacity to consent during the study. Participants must have a project partner who will consent to this role and support the participant with the study procedures.

The study intervention uses standard dental techniques and will be carried out by qualified dentists in dental practice. Dental assessments by the study team will be carried out by qualified dentists assisted by the dental nurse in appropriate facilities within the Brain Centre. None of the dental treatment should pose any risk above that posed by normal dental care.

The cognitive assessments will be carried out by a trained assessor.

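### Examiner blinding is asserted but not protected: the dental nurse who places IDC participants at treatment sites also appears to assist the dental outcome assessments

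*Protocol*

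**What the plan says.** **The blinding claim.** The Study Summary describes "An examiner blind, parallel, 2 arm randomised controlled trial". Section 4.3 names the people covered: "Both the study dentist and cognitive assessor will be blinded to the treatment received by the participant". No other role is declared blind.

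**The dental nurse.** In section 4.2.2, on the IDC group, "The study dental nurse will allocate the study participant to BDH or a DFS-GDPr taking travel time into account". In section 8.1, on the examinations at the Brain Centre, "Dental assessments by the study team will be carried out by qualified dentists assisted by the dental nurse".

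**The separation that is stated.** Section 4.1 has the outcomes assessed "by central research team study staff at study appointments that are independent of study intervention appointments".

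**Concealment.** Section 4.2.1 describes the randomisation schedule as "computer-generated, concealed from recruiter until consent obtained". Section 6.3.2 says that at screening, before any study procedure, "the cognitive assessor will go through the participant information sheet and take informed consent from the participant".

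**Timing of randomisation.** Section 4.2.1 places it after the screening appointment, when the baseline cognitive and periodontal results are both available. Footnote 2 of Appendix 1 places it on the following day. The same footnote describes the contact that tells participants their group and, for the treatment group, assigns a practice.

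**The concern.** Bleeding on probing and plaque are yes/no judgements, and pocket depth is a probe reading. All three are scored by the examiner and can shift with what the examiner knows or senses about treatment. If someone in the room knows the arm, the examiner's blinding depends on that person never disclosing it, and the protocol describes no safeguard.

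Oral-health improvement in the intervention arm is a stated objective (section 3.1). Section 4.4 uses the observed effect sizes, with 80% confidence intervals, to illustrate proof of concept and to check that the assumptions for the definitive trial are plausible. Assessment bias would pass into that planning, and analysis could not remove it afterwards.

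The concealment wording raises a smaller concern of the same kind. The stated endpoint is consent, and the person taking consent is the cognitive assessor, who has to stay blind throughout follow-up.

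**Working it through.** The plan gives no figure to reproduce here, and the point depends on no formula beyond a count. The check sets the role descriptions side by side.

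**Step 1: does the placement task require knowledge of the arm?** Yes. Under section 4.2.2 only IDC participants attend the dental hospital or a foundation-scheme practice for study treatment. Under section 4.2.3 the SDC group continues its usual care. Whoever places participants therefore has the list of Arm 1 members, and anyone enrolled but not on that list is in Arm 2.

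**Step 2: is the same role present when outcomes are scored?** Section 8.1 puts the dental nurse beside the examining dentist at the Brain Centre. Section 4.2.2 refers to the study dental nurse and section 8.1 to the dental nurse, both in the singular with a definite article, and no second study nurse for dental work is described. That they are one person is very likely but is an inference.

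**Step 3: does a stated safeguard close the route?** Section 4.1 separates assessment appointments from intervention appointments. It separates occasions, not people, so a nurse who has made the placements can still attend the assessment. Nothing says how the nurse's knowledge is kept from the dentist, who holds the allocation, or who passes it on. Section 4.2.2 also sends the IDC treatment charts to the study team without saying which members may see them.

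**Step 4: how many assessments are exposed?**

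- Participants: 50 (section 6.2).
- Follow-up visits with a dental assessment: 2, at 6 and 12 months (section 4.2.4, Appendix 1). The 18-month visit is cognitive only.
- Exposed assessments: 50 × 2 = 100 at most, fewer with any loss to follow-up.
- Baseline assessments are not counted because they precede randomisation.

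**Step 5: the order of events for concealment.** From sections 6.3.2 and 4.2.1 and Appendix 1, the order is:

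1. consent, taken by the cognitive assessor;
2. cognitive eligibility;
3. dental eligibility and enrolment;
4. baseline cognitive and periodontal scores;
5. randomisation;
6. notification of the participant.

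The stated concealment endpoint is step 1, whereas eligibility and baseline scoring are steps 2 to 4. Because randomisation is step 5, the wording does not instruct anyone to learn an allocation early. It sets the endpoint too soon, and it does not extend concealment for the consent-taker to the last assessment, as section 4.3 requires.

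**The case against.** **The claim covers examiners, and the nurse is not one.** Section 4.3 names the study dentist and the cognitive assessor. Section 8.1 has dentists carry out the assessments with the nurse only assisting, and nothing says that the nurse scores anything or tells the dentist the arm. This stands. A reader might infer that the roles contradict the blinding claim outright, but they do not: a blind dentist and an informed nurse can both be present. What remains is an unguarded route.

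**The chronology protects baseline.** A reader might infer that the cognitive assessor may know the allocation before scoring the baseline CDR-SB that sets the stratum. The documents do not support this. Randomisation uses the baseline results and follows the visit. The protocol does not define the recruiter, and sections 6.3.1 and 6.3.2 spread recruitment work over several people. Concealment up to consent states a minimum and does not say that the recruiter is told afterwards, while section 4.3 commits the cognitive assessor to blinding. The remaining defect is wording that stops too early.

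**This is a feasibility study.** Section 3.2 ties progression to recruitment and data-completion targets, which assessor blinding does not affect. The periodontal precision statement in section 6.2 concerns the 25 intervention participants and not a contrast between arms. This lowers the severity but does not remove the point. A change within one arm still compares a baseline scored before allocation with follow-up scores taken with an informed nurse present, and section 4.4 uses those effect sizes for planning.

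**The remedy assumes staffing.** The protocol does not say that the study co-ordinator is absent from assessments. This is fair, so the fix is conditional on it.

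**Conclusion.** The point holds as a gap in protecting examiner blinding, not as a demonstrated breach. Following the plan as written puts a person who must know the allocation beside the examining dentist at up to 100 follow-up dental assessments. This assumes that the nurse in sections 4.2.2 and 8.1 is the same person, which is very likely but not stated. If they are two people and the second has no access to allocation, the route closes, and the protocol need only say so.

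It may be tempting to conclude that the results would be biased towards IDC, or that all cognitive assessments are compromised. Neither follows. The direction and size of any bias cannot be derived from the document, the nurse is not described as attending cognitive assessments, and unblinding of the cognitive assessor is not prescribed anywhere.

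The concealment wording is a secondary defect: its endpoint falls before eligibility and baseline scoring and should come after them. Severity is moderate. These are matters of trial conduct that the protocol itself sets, so they would not normally be left to an analysis plan.

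**What to change.** 1. **Separate the tasks (sections 4.2.2 and 8.1).** Give site placement, the contact that tells participants their arm, and receipt of the IDC dental charts to an existing team member who does not attend assessments. The study co-ordinator would suit if not present at them. Alternatively, keep placement with the study dental nurse and have a nurse without allocation knowledge assist the assessments.
2. **Correct the concealment endpoint (section 4.2.1).** Suggested text: *Allocation is concealed until eligibility and all baseline scores have been recorded. It is then released only to the team member responsible for placement. The study dentist, the nurse assisting the assessments and the cognitive assessor remain blind until the participant's last assessment.*
3. **Order the 12-month visit.** Section 4.3 and Appendix 1 place a participant interview at this visit, while section 5 describes the qualitative work as online. Any interview held at the visit should follow both the dental and the cognitive assessment and be conducted by someone who is not an assessor.

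The cost is one administrative task reassigned and a few sentences reworded, with slightly more work for whoever takes it over. Sample size, visits and treatment do not change. If no existing team member is free of assessment duties, the second option in item 1 would require a different nurse at the assessments.
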